# **10.3.2** Surgery Visit (Visit 00 and Visit 00A)

# Visit 00: Day 0 (implant for first eye)

# Visit 00A: 7-14 days after surgery for Eye 1 (implant for second eye)

Below is a list of study procedures to be undertaken at the surgery visit. Procedures should be performed in the order presented below. Activities involving multiple delegated staff members may be performed in parallel. All assessments must be recorded in source documentation and eCRFs (if applicable).

# Procedures performed in ORA group:

- Subjects will be randomized and undergo surgery using the ORA system.
- Document any changes to ocular and nonocular concomitant medications.
- Prepare subject/operative eye for surgery in accordance with site-specific operating procedures.
- Ensure that the subject was randomized to ORA and it is utilized for the surgery.
- Perform the surgical procedure using standard of care.
- Record aphakic refraction and aphakic SE.
- Record IOL power recommended by ORA and predicted post-operative SE.
- Record implanted IOL power and predicted post-operative SE.
- Record any surgical problems, complications, or other procedures that occur during surgery.
- Record any device deficiencies and adverse events. Refer to Section 11 for further detail.

# **Procedures performed in Barrett Toric Calculator group:**

- Subjects will be randomized and undergo surgery using the Barrett Toric Calculator.
- Take preoperative measurements for IOL calculation.
- Prepare subject/operative eye for surgery in accordance with site-specific operating procedures.
- Document any changes to ocular and nonocular concomitant medications.
- Ensure that the subject was randomized to Barrett Toric Calculator and it is utilized.
- Perform surgical procedure using standard of care.
- Record implanted IOL power and anticipated residual refractive astigmatism.
- Record any surgical problems, complications, or other procedures that occur during surgery.
- Record any device deficiencies and adverse events. Refer to Section 11 for further detail.

# 10.3.3 Visit 1/1A (Day 1 for Eye 1/2)

• Document any changes to ocular and nonocular concomitant medications.

• Record any device deficiencies and adverse events. Refer to Section 11 for further detail.

# 10.3.4 Post-Surgery Visit (Visits 2, 2A, 3A, 4A and 5A)

Below is a list of study procedures to be undertaken at post-surgery visits. Procedures should be performed in the order presented below. All assessments must be recorded in source documents and eCRFs (if applicable).

ł	
•	Document changes in ocular and nonocular concomitant medications at Visits 2, 2A, 3A, 4A, and 5A.
•	
•	Perform BCDVA (monocular) assessment at Visits 2, 2A, 3A, 4A, and 5A. Refer to MOP for details.
•	

- - Record any device deficiencies and AEs. Refer to Section 11 for further detail.
- Document subject exit from study at Visit 5A.

# **10.4 Unscheduled Visits**

If a subject visit occurs between any regularly scheduled visits, this visit must be documented as an Unscheduled Visit. During all unscheduled visits, the Investigator must conduct the following procedures:

- Collect Adverse Event information
- Record changes in medical condition or concomitant medication

The Investigator may perform additional procedures for proper diagnosis and treatment of the subject. The Investigator must document this information in the subject's case history source documents.

If during an Unscheduled Visit the subject is discontinuing from the study, the Investigator must conduct Exit procedures according to Table 3-1 Schedule of Study Procedures and Assessments, as possible.

# **10.5 Discontinued Subjects**

# 10.5.1 Screen Failures

Subjects who were excluded from the study after signing the informed consent and prior to randomization/surgical procedure.

The Investigator must document the reason for screen failure in the subject's case history source documents.

Subject numbers must not be re-used.

# **10.5.2 Discontinuations**

Discontinued subjects are individuals who voluntarily withdraw or are withdrawn from the study by the Investigator after randomization/surgical procedure.

Subject numbers of discontinued subjects must not be re-used.

Page 52 of 70

Subjects may discontinue from study or study treatment at any time for any reason. Subjects may also be discontinued from study treatment at any time if, in the opinion of the Investigator, continued treatment poses a risk to their health.

If a subject discontinues from study treatment, every effort must be made to keep the subject in the study and to continue with the study assessments as specified in the schedule of study procedures and assessments until the final visit.

For subjects discontinuing from the study, the Investigator must complete all Exit procedures according to Table 3-1 Schedule of Study Procedures and Assessments, if the subject is willing and able, and if in the opinion of the Investigator it is safe for the subject to do so.

The Investigator must document the reason for study or treatment discontinuation in the subject's case history source documents.

To ensure the safety of all subjects who discontinue early, Investigators must assess each subject and, if necessary, advise them of any therapies and/or medical procedures that may be needed to maintain their health.

# 10.5.3 Schedule of Procedures and Assessments for Subjects Discontinued from Investigational Product

Not applicable.

# **10.6 Clinical Study Termination**

The Study Sponsor reserves the right to close the investigational site or terminate the study in its entirety at any time.

If the clinical study is prematurely terminated or suspended by the Study Sponsor:

- The Study Sponsor must:
  - Immediately notify the Investigator(s) and subsequently provide instructions for study termination.
  - Inform the Investigator and the regulatory authorities of the termination/suspension and the reason(s) for the termination/suspension.
- The Investigator must:
  - Promptly notify the IRB/IEC of the termination or suspension and of the reasons.

Page 53 of 70

Provide subjects with recommendations for post-study treatment options as needed.

The Investigator may terminate the site's participation in the study for reasonable cause.

# 10.6.1 Follow-up of subjects after study participation has ended

Following this study, the subject will return to their eye care professional for their routine eye care.

# **11 ADVERSE EVENTS AND DEVICE DEFICIENCIES**

# **11.1 General Information**

An AE is any untoward medical occurrence, unintended disease or injury, or untoward clinical signs (including abnormal laboratory findings) in subjects, users, or other persons, whether or not related to the investigational medical device (test article). Refer to the Glossary of Terms for categories of AEs and SAEs.

## Figure 11–1 **Categorization of All Adverse Event**

Page 54 of 70

## Figure 11–2

## Categorization of All Serious Adverse Events

# 11.1.1 Specific Events Relevant to this Protocol

There are no specific adverse events included in this protocol.

In addition to all AEs [serious (excluding posterior capsulotomy performed for PCO) and nonserious] meeting the definitions, any potentially sight-threatening event may be considered serious based on the judgment of the Investigator and should be reported appropriately as delineated in Section 11.3.

# 11.1.2 Device Deficiencies

A device deficiency may or may not be associated with subject harm (ie, ADE or SADE); however, not all ADEs or SADEs are due to a device deficiency. The Investigator should determine the applicable category for the identified or suspect device deficiency and report any subject harm separately.

# 11.2 Monitoring for Adverse Events

At each visit, after the subject has the opportunity to spontaneously mention any problems, the Investigator should inquire about AEs by asking the standard questions:

• "Have you had any health problems since your last study visit?"

• "Have there been any changes in the medicines you take since your last study visit?"

Changes in any protocol-specific parameters and/or questionnaires evaluated during the study are to be reviewed by the Investigator. Any untoward (unfavorable and unintended) change in a protocol-specific parameter or questionnaire response that is clinically relevant, in the opinion of the Investigator, is to be reported as an AE. These clinically relevant changes will be reported regardless of causality.

# **11.3 Procedures for Recording and Reporting**

Adverse events are collected from the time of informed consent. Any pre-existing medical conditions or signs/symptoms present in a subject prior to the start of the study (ie, before informed consent is signed) are not considered AEs in the study and should be recorded in the Medical History section of the eCRF.

In addition, aqueous cells and flare, corneal edema, raised IOP and superficial punctate keratitis are examples of early postoperative findings that are typically observed following ocular surgery. These are not considered AEs if they can be reasonably expected to resolve within a week and not result in any untoward long term visual outcome impact.

For each recorded event, the ADE and SAE documentation must include the following: date of occurrence, severity, treatment (if applicable), outcome, and assessments of the seriousness, and causality. In addition, the Investigator must document all device deficiencies reported or observed with test articles on the Device Deficiency eCRF. The site must submit all available information on ADEs, SAEs, and device deficiencies to the Study Sponsor immediately as follows:

- All SAEs must be reported immediately (within 24 hours) of the Investigator's or site's awareness.
- ADEs that do not meet seriousness criteria and device deficiencies must be reported within 10 calendar days of the Investigator's or site's awareness.
- A printed copy of the completed Serious Adverse Event and Adverse Device Effect and/or Device Deficiency eCRF must be included with product returns.
- Additional relevant information after initial reporting must be entered into the eCRF as soon as the data become available.
- Document any changes to concomitant medications on the appropriate eCRFs.

Page 56 of 70

• Document all relevant information from Discharge Summary, Autopsy Report, Certificate of Death, etc, if applicable, in narrative section of the Adverse Device Effect (for related AEs) and Serious Adverse Event eCRF.

*Note:* Should the EDC system become non-operational, the site must complete the appropriate paper *Serious Adverse Event and Adverse Device Effect* and/or *Device Deficiency Form.* The completed form is emailed to the Study Sponsor to [name] according to the timelines outlined above; however, the reported information must be entered into the EDC system once it becomes operational.

Any AEs and device deficiencies for non-study marketed devices/products (ie, AcrySof IQ Toric IOL SN6AT3-6, Alcon OVDs and BSS and Alcon surgical systems) will be considered and processed as spontaneous (following the post-market vigilance procedures) and should be communicated to the device's/product's manufacturer as per local requirements.

Study Sponsor representatives may be contacted for any protocol related question and their contact information is provided in the Manual of Procedures that accompanies this protocol.

Further, depending upon the nature of the AE or device deficiency being reported, the Study Sponsor may request copies of applicable portions of the subject's medical records. The Investigator must also report all AEs and device deficiencies that could have led to a SADE according to the requirements of regulatory authorities or IRB/IEC.

# **11.3.1 Intensity and Causality Assessments**

Where appropriate, the Investigator must assess the intensity (severity) of the AE based on medical judgment with consideration of any subjective symptom(s), as defined below:

# Intensity (Severity)

Mild	An AE is mild if the subject is aware of but can easily tolerate the sign or symptom.
Moderate	An AE is moderate if the sign or symptom results in discomfort significant enough to cause interference with the subject's usual activities.
Severe	An AE is severe if the sign or symptom is incapacitating and results in the subject's inability to work or engage in their usual activities.

For every AE in the study, the Investigator must assess the causality (Related or Not Related to the medical device or study procedure). An assessment of causality will also be performed by Study Sponsor utilizing the same definitions, as shown below:

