# **1 GLOSSARY OF TERMS**

Name of Test product(s)	ORA System with VerifEye+
Name of Test Product(s)	Alcon Toric Calculator (Barrett)
Adverse Device Effect	Adverse event related to the use of an investigational medical device (test product) or control product. Note: This definition includes adverse events resulting from insufficient or inadequate instructions for use, deployment, implantation, installation, or operation; any malfunction; and use error or intentional misuse of the test product or control product.
Adverse Event	Any untoward medical occurrence, unintended disease or injury, or untoward clinical signs (including abnormal laboratory findings) in subjects, users or other persons, whether or not related to the investigational medical device (test product). Note: For subjects, this definition includes events related to the test product, the control product, or the procedures involved. For users or other persons, this definition is restricted to events related to the test product. Requirements for reporting Adverse Events in the study can be found in Section 11.
Anticipated Serious Adverse Device Effect	Serious adverse device effect which by its nature, incidence, severity, or outcome has been identified in the risk management file.
Device Deficiency	
 
Inadequacy of a medical device with respect to its identity, quality, durability, reliability, safety, or performance. Note: This definition includes malfunctions, use errors, and inadequate labeling.
 
Requirements for reporting Device Deficiencies in the study can be found in Section 11.
 

**Document:** TDOC-0055329 **Status:** Effective

Enrolled Subject	Any subject who signs an informed consent form for participation in the study.
Interventional Clinical Trial	A research trial that prospectively assigns, whether randomly or not, human participants or groups of humans to one or more health-related interventions to evaluate the effects on health outcomes, and/or a research trial in which diagnostic or monitoring procedures beyond standard of care are conducted and generate outcomes for use in analysis of data.

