## Safety Objective(s) 6.4

Table 6–3Safety Objective(
----------------------------

Objective(s)	Endpoint(s)
Evaluation of adverse events including secondary surgical interventions related to the investigational device	Adverse events
Device deficiencies	Device deficiencies

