# Causality

Related	An AE classified as related may be either definitely related or possibly related		
	where a direct cause and effect relationship with the medical device or study		
	procedure has not been demonstrated, but there is a reasonable possibility that		
	the AE was caused by the medical device or study procedure.		
Not Related	An AE classified as not related may either be definitely unrelated or simply		
	unlikely to be related (ie, there are other more likely causes for the AE).		

The Study Sponsor will assess the AEs and may upgrade the Investigator's assessment of seriousness and/or causality. The Study Sponsor will notify the Investigator of any AEs that is upgraded from non-serious to serious or from unrelated to related.

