5.3 Statistical Methods for Safety Analyses

5.3.1 Advserse Events including SSIs

All information obtained on adverse events (AEs) will be displayed by treatment and subject. The number and percentage of all ocular adverse events, including secondary surgical interventions (SSIs) will be tabulated by preferred term with a breakdown by treatment. An eye with multiple ocular AEs of the same preferred term will be only counted once toward the total of this preferred term.

The number and percentage of all adverse events will also be tabulated with a breakdown by treatment.

Adverse events will be summarized in the following tables:

- 1. All Adverse Events (Serious and Non-Serious Combined)
 - a. Ocular
 - b. Nonocular
- 2. All Adverse Device Effects
 - a. Ocular
 - b. Nonocular
- 3. All Serious Adverse Events (including Serious Adverse Device Effects)
 - a. Ocular
 - b. Nonocular
- 4. Subject Listings

- a. Non-Serious Ocular
- b. Non-Serious Nonocular
- c. Serious Ocular
- d. Serious Nonocular

In addition, the number and percentage of secondary surgical interventions will be presented

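### The protocol's only causality judgement pools device and procedure, so procedure-only events could enter the adverse device effect tables, which the Glossary limits to device-related events

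*Protocol*

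**What the plan says.** **Causality rule.** Under Protocol 11.3.1, for every AE, "the Investigator must assess the causality (Related or Not Related to the medical device or study procedure"). The definition of Related asks for a reasonable possibility that "the AE was caused by the medical device or study procedure". For the sponsor's review, "An assessment of causality will also be performed by Study Sponsor utilizing the same definitions". The sponsor changes described there are upgrades only, one of them from unrelated to related.

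**Form.** Protocol 11.3 tells sites to place information from documents such as discharge summaries in the "narrative section of the Adverse Device Effect (for related AEs) and Serious Adverse Event eCRF".

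**Definition of an ADE.** Protocol Section 1 (Glossary) reads: "Adverse event related to the use of an investigational medical device (test product) or control product". Its note adds faults in instructions or operation, malfunction and use error. It does not name the surgical procedure as such.

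**Objective.** Protocol 6.4, Table 6-3 reads: "Evaluation of adverse events including secondary surgical interventions related to the investigational device". The Protocol Summary and SAP 1.1 say the same in substance.

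**Output.** SAP 5.3.1 lists a table set called "All Adverse Device Effects", split into ocular and nonocular, with no rule for deriving ADE status. It also promises a count and percentage of SSIs. No split by relatedness is visible.

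**The concern.** The plan reports a device-specific quantity but defines only a judgement that is not device-specific. Every study eye has cataract surgery. An investigator who believes that a complication came from the surgery, and not from the aberrometer or the calculator, still has grounds to answer Related under 11.3.1. If that answer then sets ADE status, the ADE tables mix device effects with surgical events common to both groups.

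Three things would be at stake:

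- the level of the ADE rate reported for each technique;
- the relative comparison between a technique that adds intraoperative measurement (ORA) and one used before surgery (the calculator);
- the reporting path, because non-serious ADEs carry a 10-calendar-day reporting deadline under Section 11.3.

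The device-related part of the safety objective, including SSIs, would have no clean source in the defined data.

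**Working it through.** The documents state no figure for this point, so the main check is a comparison of the texts.

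**Step 1. Does any rule isolate the device?**

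| Place | Cause covered |
|---|---|
| Protocol 11.3.1, investigator | device or procedure, one answer |
| Protocol 11.3.1, definition of Related | device or procedure |
| Protocol 11.3.1, sponsor review | same definitions |
| Protocol 11.3, label on the ADE eCRF | related AEs |
| Protocol Section 1, ADE | device only |
| Protocol 6.4 and SAP 1.1, objective | device only |
| SAP 5.3.1, ADE tables | named as device effects, no derivation rule |

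The definitions and outputs are device-specific, but the judgement meant to feed them is not.

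**Step 2. Is cataract surgery a study procedure?** The term is not defined. However, cataract surgery is a row in the schedule of procedures (Table 3-1). Section 10.3.2 presents its surgery-visit steps as study procedures, and both groups' lists include performing the operation. Reading 11.3.1 to cover surgical complications is therefore reasonable.

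**Step 3. Do the exemptions in Section 11.3 remove the problem?** One exempts listed early findings, such as corneal edema and raised IOP, if they can be expected to resolve within a week with no lasting visual effect. The other sends AEs of non-study marketed products (the IOL, OVDs, BSS and surgical systems) to spontaneous reporting. Neither covers a longer-lasting complication attributed to the surgery itself.

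**Step 4. Illustration of the effect (assumed rates).** Let *p* be the device-related AE rate per eye and *q* a procedure-related rate equal in both groups and independent of *p*. The pooled rate is 1 − (1 − *p*)(1 − *q*). Take *p* = 1% and 3%. For *q* = 5%:

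- 1 − 0.99 × 0.95 = 5.95%
- 1 − 0.97 × 0.95 = 7.85%

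| *q* | Group 1 | Group 2 | Ratio | Difference (points) |
|---|---|---|---|---|
| 0% | 1.00% | 3.00% | 3.0 | 2.00 |
| 2% | 2.98% | 4.94% | 1.66 | 1.96 |
| 5% | 5.95% | 7.85% | 1.32 | 1.90 |
| 10% | 10.9% | 12.7% | 1.17 | 1.80 |

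The difference equals (3% − 1%)(1 − *q*), so it shrinks only slightly. The levels and the ratio change materially.

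**Step 5. Effect on one group's rate (assumed counts).** Take 90 eyes in a group with no device-related event. The correct ADE entry is 0/90 = 0% (exact 95% CI 0% to 4.0%). If 4 or 5 procedure-only events were included, the entry would be 4/90 = 4.4% (1.2% to 11.0%) or 5/90 = 5.6% (1.8% to 12.5%).

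**The case against.** The strongest reply is that the Glossary governs. ADE is a defined term, so a procedure-only event is not an ADE wherever the term appears, including in SAP 5.3.1. The eCRF label sits in a bullet about where narrative information goes and does not set ADE status. Figures 11-1 and 11-2, which categorize AEs and SAEs, are not reproduced in the text reviewed. The eCRF and Manual of Procedures were not available either. Any of these may separate the two causes. The SAP sentence on SSIs ends without a full stop, so text may have been removed there.

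Much of this stands, and it rules out three stronger readings that a reader might infer:

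- **Every related AE is entered as an ADE, so surgical complications are counted as device effects.** No rule says so. It is an inference from a parenthesis and conflicts with the Glossary. The documents support only that such events could be counted.
- **The safety question cannot be answered.** The endpoints are AEs and device deficiencies without restriction to related events. All AEs and SAEs are tabulated by treatment, and subject listings are provided, whatever the ADE flag says.
- **A real difference between techniques would be hidden.** In the illustration the absolute difference falls only from 2.00 to 1.80 points even at a 10% procedure rate.

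The reply does not remove the mismatch. A device-only definition needs a device-only judgement, and the available text defines none.

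**Conclusion.** The point holds as an inconsistency with a possible consequence. The pooled causality judgement and the eCRF label do not fit the device-only ADE definition and the device-related objective. Surgical complications outside the Section 11.3 exemptions could therefore be tabulated as ADEs. If they were, ADE rates would rise in both groups and the ratio between them would shrink.

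The size cannot be determined, because the documents give no AE rates and every rate and count in the illustrations is assumed. The conclusion also assumes that the operation counts as a study procedure, which the schedule and Section 10.3.2 support but no definition confirms, and that no unseen material already separates the causes. The practical weight is moderate: safety is descriptive, with no hypotheses, and only the ADE tables and the device-related reading of SSIs are exposed.

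**What to change.** 1. In Protocol 11.3.1 and in the sponsor's review, replace the single answer with two: related to the test device (ORA or calculator), and related to the surgical procedure. Make the same change in the eCRF if it does not already hold both.
2. In Protocol 11.3, describe the ADE eCRF as being for device-related AEs.
3. In SAP 5.3.1, state that the ADE tables use the device answer only, in line with the Glossary.
4. In SAP 5.3.1, present SSIs overall and as the device-related subset.

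The cost is protocol and SAP wording, slightly more data entry per AE, and one extra split in the tables. If the eCRF already separates the causes, only the wording and the table rules need to be aligned.
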